#### ORR and CBR

ORR and CBR will be summarized using descriptive statistics (N, %) along with two-sided exact binomial 95% CIs (Clopper and Pearson 1934).

#### ECOG performance status

The ECOG PS scale (Table 2-4 will be used to assess physical health of patients, ranging from 0 (most active) to 5 (least active):

Table 2-4	ECOG Performance Scale
Score	Description
0	Fully active, able to carry on all pre-disease performance without restriction
1	Restricted in physically strenuous activity but ambulatory and able to carry out work of a light or sedentary nature, e.g., light house work, office work
2	Ambulatory and capable of all self-care but unable to carry out any work activities. Up and about more than 50% of waking hours
3	Capable of only limited self-care, confined to bed or chair more than 50% of waking hours
4	Completely disabled. Cannot carry on any self-care. Totally confined to bed or chair
5	Dead

Frequency counts and percentages of patients in each score category will be provided by time point based on the windows defined in Section 2.1.

Novartis	Confidential	Page 31
SAP	22-Feb-2022 (1:27)	CLEE011A2404

#### Proportion of patients with clinical benefit in the Extension Phase

Proportion of patients with clinical benefit as assessed by the investigator will be summarized at scheduled visits. Clinical benefit will be summarized using the Safety Set in Extension Phase.

#### 2.7.3 Handling of missing values/censoring/discontinuations

TTP will be censored at the date of the last adequate tumor assessment if no TTP event is observed prior to the analysis cut-off date or the date when a new anti-neoplastic therapy or another investigational treatment for cancer is started, whichever occurs earlier. The censoring date will be the date of last adequate tumor assessment.

The date of last adequate tumor assessment is the date of the last tumor assessment with overall lesion response of CR, PR or SD before an event or a censoring reason occurred. In this case the last tumor evaluation date at that assessment will be used. If no post-baseline assessments are available (before an event or a censoring reason occurred) then the start date of treatment will be used.

In particular, TTP will be censored at the last adequate tumor assessment if one of the following occurs: absence of event, the event occurred after two or more missing tumor assessments. The term "missing adequate tumor assessment" is defined as a tumor assessment (TA) not performed or tumor assessment with overall lesion response of "UNK". The rule to determine number of missing TAs is based on the time interval between the date of last adequate tumor assessment and the date of an event.

## 2.8 Safety analyses

All safety analyses for the Core Phase will be based on the safety set in Core Phase.

#### 2.8.1 Adverse events

AE summaries will include all AEs occurring during on treatment period. All AEs collected in the AE eCRF page will be listed along with the information collected on those AEs e.g. AE relationship to study drug, AE outcome etc. AEs with start date outside of on-treatment period will be flagged in the listings.

AEs will be summarized by number and percentage of patients having at least one AE, having at least one AE in each primary system organ class (SOC) and for each preferred term (PT) using MedDRA coding. A patient with multiple occurrences of an AE will be counted only once in the respective AE category. A patient with multiple Common Terminology Criteria for Adverse Events (CTCAE) grades for the same preferred term will be summarized under the maximum CTCAE grade recorded for the event. AE with missing CTCAE grade will be included in the 'All grades' column of the summary tables.

In AE summaries, the primary system organ class will be presented alphabetically and the preferred terms will be sorted within primary SOC in descending frequency. The sort order for the preferred term will be based on their frequency.

Novartis	Confidential	Page 32
SAP	22-Feb-2022 (1:27)	CLEE011A2404

The following adverse event summaries will be produced; overview of adverse events and deaths, AEs by SOC and PT, summarized by relationship, seriousness, leading to treatment discontinuation, leading to dose interruption/adjustment, requiring additional therapy and leading to fatal outcome. In addition, a summary of serious adverse events with number of occurrences will be produced (an occurrence is defined as >1 day between start and prior end date of record of same preferred term).

## 2.8.2 Adverse events of special interest / grouping of AEs

The AEs of Special Interest (AESIs) includes: Neutropenia including febrile neutropenia, QT prolongation, and hepatobiliary AEs.

A Case Retrieval Sheet (CRS; an Excel file) with the exact composition of the adverse events groupings is to be used to map reported adverse events to the AESIs groupings (termed Specific Event Categories (SECs) in the CRS). This file may be updated (i.e. it is a living document) based on review of accumulating trial data.

## Analysis of AESIs

An adverse event of special interest is a grouping of adverse events that are of scientific and medical concern specific to compound ribociclib. These groupings are defined using MedDRA terms, SMQs (standardized MedDRA queries), HGLTs (high level group terms), HLT (high level terms) and PTs (preferred terms). Customized SMQs (Novartis MedDRA queries, NMQ) may also be used. A NMQ is a customized group of search terms which defines a medical concept for which there is no official SMQ available or the available SMQ does not completely fit the need. It may include a combination of single terms and/or an existing SMQ, narrow or broad. For each specified AESI, number and percentage of patients with at least one event of the AESI occurring during on treatment period will be summarized.

Summaries of these AESIs will be provided, (specifying grade, SAE, relationship, leading to treatment discontinuation, leading to dose adjustment/interruption, hospitalization, death etc.). If sufficient number of events occurred, analysis of time to first occurrence will be applied.

A listing of all grouping levels down to the MedDRA preferred terms used to define each AESI will be generated.

## 2.8.3 Deaths

Separate summaries for on-treatment and all deaths will be produced by system organ class and preferred term. All deaths will be listed, post treatment deaths will be flagged.

## 2.8.4 Laboratory data

On analyzing laboratory, data from all sources (local laboratories) will be combined. The summaries will include all assessments available for the lab parameter collected no later than 30 days after the last study treatment administration date (see Section 2.1.1).

The following summaries will be produced for hematology and biochemistry laboratory data (by laboratory parameter and treatment):

Novartis	Confidential	Page 33
SAP	22-Feb-2022 (1:27)	CLEE011A2404

- Worst post-baseline CTC grade (regardless of the baseline status). Each patient will be counted only for the worst grade observed post-baseline.
- Shift tables using CTC grades to compare baseline to the worst on-treatment value
- For laboratory tests where CTC grades are not defined, shift tables using the low/normal/high/(low and high) classification to compare baseline to the worst on-treatment value.
- Trends of lab parameter values over time (baseline and selected on-treatment timepoints) should be displayed via boxplots based on time windows and corresponding tables displaying the statistics used for the box plots by the selected time points.

The following listings will be produced for the laboratory data:

- Listings of all laboratory data, with CTC grades and classification relative to the laboratory normal range. Lab data collected during the post-treatment period will be flagged.
- Listing of all CTC grade 3 or 4 laboratory toxicities

#### Liver function parameters

Liver function parameters of interest are total bilirubin (TBL), ALT, AST and alkaline phosphatase (ALP). The number (%) of patients with worst post-baseline values as per Novartis Liver Toxicity guidelines will be summarized:

The following summaries will be produced:

- ALT or AST > 3xULN
- ALT or AST > 5xULN
- ALT or AST > 8xULN
- ALT or AST > 10xULN
- ALT or AST > 20xULN
  - TBL > 2xULN
  - TBL > 3xULN
  - ALT or AST > 3xULN & TBL > 2xULN
  - ALT or AST > 3xULN & TBL > 2xULN & ALP < 2xULN

#### 2.8.5 Other safety data

#### 2.8.5.1 ECG and cardiac imaging data

#### Data analysis

12-lead ECGs including QTcF and intervals will be obtained locally for each patient during the study. ECG data will be read and interpreted locally.

The number and percentage of patients with notable ECG values will be presented

- QTcF,
  - New value of > 450 and  $\le 480$  ms
  - New value of > 480 and  $\le 500$  ms
  - New value of > 500 ms
  - Increase from Baseline of  $> 30 \text{ ms to} \le 60 \text{ms}$
  - Increase from Baseline of > 60 ms

Summary statistics will be provided for change from baseline ECG by timepoint. Time windows for ECG assessment are the same as the time windows for ECOG PS assessment (please refer to Table 2-1). If more than one assessment is done within the same time window, the worst case will be used. A listing of all ECG assessments will be produced and notable values will be flagged. In the listing, the assessments collected during the post-treatment period will be flagged.

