6.3.1.3.3 Additional follow-up for QTc prolongation

- Assessing cardiovascular dysfunction or impaired liver oxygenation, including hypotension or right heart failure as possible etiologies for liver dysfunction.
- Consider a liver biopsy as clinically indicated to assess pathological change and degree of potential liver injury

All cases of DILI confirmed on repeat testing meeting the laboratory criteria defined above, with no other alternative cause for LFT abnormalities identified, should be considered as "medically significant", thus meeting the definition of SAE (Section 8.2.1), and must be reported as SAE using the term "potential drug-induced liver injury". All events must be followed up with the outcome clearly documented. Results of tests as well as other clinically important information will be recorded in the eCRF.

Grade	Dose Modification	
For All Grades	1. Check the quality of the ECG and the QT value and repeat if needed.	
	 Perform analysis of serum electrolytes (K+, Ca++ correct for albumin, Phos, Mg++). If outside of the normal range, interrupt ribociclib administration, correct with supplements or appropriate therapy as soon as possible, and repeat electrolytes until documented as normal. 	
	 Review concomitant medication usage for the potential to inhibit CYP3A4 and/or to prolong the QT interval. 	
	4. Check compliance with correct dose and administration of ribociclib.	
1 QTcF 450-480 ms	Perform steps 1-4 as directed in "For All Grades." No dose adjustment required.	
2	Interrupt ribociclib. Perform steps 1-4 as directed in "For All Grades."	
QTcF 481-500 ms	Perform a repeat ECG within one hour of the first QTcF of \geq 481 ms.	
	Repeat ECG as clinically indicated until the QTcF returns to < 481 ms. Restart ribociclib with dose reduced by 1 dose level. Refer to Table 6-2 for dosing schedule.	
	If QTcF \ge 481 ms recurs, ribociclib should be reduced again by 1 dose level.	
	Repeat ECG 7 days and 14 days after dose resumption (then as clinically indicated) for any patients who had therapy interrupted due to $QTcF \ge 481$ ms	
3	Interrupt ribociclib. Perform steps 1-4 as directed in "For All Grades."	
QTcF ≥ 501 ms on at least	Perform a repeat ECG within one hour of the first QTcF of \geq 501 ms.	
two separate ECGs	If QTcF remains \ge 501 ms, consult with a cardiologist (or qualified specialist) and repeat cardiac monitoring as indicated until the QTcF returns to < 481 ms.	

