7.1 Study flow and visit schedule

Table 7-1 lists all of the assessments and indicates with an "X", the visits when they are performed. All data obtained from these assessments must be supported in the patient's source documentation. The table indicates which assessments produce data to be entered into the clinical database (D) or remain in source documents only (S) ("Category" column).

Note:

- During screening visits, lab assessments including white blood cell (WBC) count, absolute neutrophil count (ANC), absolute lymphocyte count, hemoglobin, platelets, INR, ALT, AST, total bilirubin (or direct bilirubin if Gilbert's Syndrome), serum creatinine, electrolytes (potassium, sodium, calcium corrected for serum albumin, and magnesium) are required to be collected within 14 days of C1D1 for eligibility assessment.
- During treatment phase, only selected labs assessments are required to be collected in the clinical database at the patient scheduled visits: WBC, ANC, absolute lymphocyte count,

hemoglobin, platelets, AST, ALT, ALP, total bilirubin, and direct bilirubin (if clinically indicated). Electrolytes should be monitored at the beginning of each cycle before resuming ribociclib dose during the first 6 cycles and as clinically indicated thereafter. The results should not be captured in clinical database. Eventual abnormal electrolyte lab results should be reported as AEs at the investigator's discretion.

- ECG will be performed at screening (within 5 days of C1D1), C1D15, C2D1, then as clinically indicated, and EOT.
- If treatment is withheld at any time during the study, all study visits, safety assessments, and efficacy assessments should be adjusted accordingly to match the treatment cycles.
- For all visits, there is a +/-3 day window on assessments to take into account scheduling over public holidays, if not explicitly specified otherwise.

Novartis	
Amended Protocol Version 04 (Clean)	

Confidential

Table 7-1	Visit evaluation	schedule	(Core Phase)
-----------	------------------	----------	-------------	---

	Category	Reference to Protocol Section	Screening Phase	Core	Core Treatment Phase						End of study treatment (EOT) within 7 days from the last dose of study treatment	Safety follow up within 30 days of last dose of study treatment		
Visit name			Screening (-28 Days to Day 1)	C1D1	C1D15	C2D1	C2D15	C3D1	C4D1	C5D1	C6D1-C11D1	C12D1 and subsequent cycles (up to cycle 36)		
Screening														
Study Informed Consent	D	7	×											

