#### Table 2-1Time window for ECOG PS assessments

Assessment	Target day of assessment	Time interval
Baseline		≤ Day 1
Cycle 2 Day 1	29	Day 2 to Day 42
Cycle 3 Day 1	57	Day 43 to Day 70
Cycle 4 Day 1	85	Day 71 to Day 98
Cycle 5 Day 1	113	Day 99 to Day 126
Cycle 6 Day 1	141	Day 127 to Day 168
Cycle 8 Day 1	197	Day 169 to Day 224
Cycle 10 Day 1	253	Day 225 to Day 280
Cycle 12 Day 1	309	Day 281 to Day 350
Every 3 cycles thereafter		
Cycle k Day 1 (k = 15, 18, …, 36)	d=(k-1)*28+1	Day d-42 to Day d+41
End of Treatment		Assessment taken at the end of treatment visit

Time windows will be defined for descriptive summary of PRO data by visit and longitudinal data analysis. Data obtained at the end of treatment will be classified as other assessment in the corresponding time window. Note that only data collected under treatment (i.e. while the patient is treated) will be included in the time to definitive deterioration or longitudinal model analysis. Post-treatment data will be summarized separately. The end of treatment assessment will be included if collected within 30 days of the last dose intake. Time windows for PRO assessment (please refer to Table 2-1) is the same as the Time windows for ECOG PS assessment.

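### Apart from end of treatment, 15 of the 16 cycle windows in the ECG change-from-baseline table hold essentially only unscheduled ECGs and cannot show the cohort's course

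*SAP*

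**What the plan says.** SAP 2.8.5.1 plans a descriptive display: "Summary statistics will be provided for change from baseline ECG by timepoint". It creates no ECG-specific windows: "Time windows for ECG assessment are the same as the time windows for ECOG PS assessment". It also departs from the general rule in SAP 2.1.4, which takes the assessment nearest the target day. For ECG, "If more than one assessment is done within the same time window, the worst case will be used". SAP 2.1.4 slots unscheduled visits into the windows as well.

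SAP Table 2-1 lists Cycles 2, 3, 4, 5, 6, 8, 10 and 12, then "Every 3 cycles thereafter" up to Cycle 36, each of these later windows running "Day d-42 to Day d+41". A separate final row is defined as "Assessment taken at the end of treatment visit".

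The protocol's ECG schedule is much shorter. Section 7.1 requires a screening ECG and then "C1D15, C2D1, then as clinically indicated, and EOT"; Table 7-1 and section 7.2.2.6.1 agree. Other on-treatment ECGs arise in four ways:

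- clinical indication (7.1, 7.2.2.6.1);
- investigator discretion (7.2.2.6.1);
- monitoring when certain co-medications are needed (6.4.4);
- follow-up of QTcF of 481 ms or more under Table 6-5, including "Repeat ECG 7 days and 14 days after dose resumption (then as clinically indicated").

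**The concern.** The ECOG windows suit ECOG status because it is assessed at those cycle visits in every patient still on treatment. ECGs are not. A row headed Cycle 8 Day 1 or Cycle 24 Day 1 invites the reader to take its mean as the treated cohort's QTcF change at that time, and to read a trend down the column. Yet patients enter such a row because someone had a reason to record an ECG, and the reasons and the patients differ from row to row.

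QT prolongation is an adverse event of special interest within the primary endpoint, and there is no control arm against which to judge a late-cycle mean. Protocol 4.3 supports the follow-up length partly by noting that QTc prolongation in the earlier phase III trial appeared in the first two cycles. Rows out to Cycle 36 would seem to describe later QT behaviour, which this schedule cannot do. SAP 2.8.5.1 contains no restriction to scheduled visits, no minimum number per row and no caveat. The general list of statistics for quantitative data in SAP 2.1.2 does not name n.

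**Working it through.** **1. Reproduce the windows.** With target day d = (k − 1) × 28 + 1, k = 2, 3, 4, 5, 6, 8, 10, 12 gives Days 29, 57, 85, 113, 141, 197, 253, 309, as printed in Table 2-1. For k = 15, 18, 21, 24, 27, 30, 33, 36 the formula gives Days 393 to 981. That is 8 + 8 = 16 post-baseline cycle windows, contiguous from Day 2 to Day 1022 (981 + 41). From Cycle 15 each window spans 42 + 1 + 41 = 84 days.

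**2. Place the scheduled ECGs.** C1D15 is Day 15 and C2D1 is Day 29, each ± 3 days (Protocol 7.1). Both fall in the Cycle 2 window, Day 2 to 42. No other cycle window contains a scheduled ECG, so 16 − 1 = 15 have none. Counting the EOT row, which does have one, it is 15 of 17 post-baseline rows. A delayed Cycle 2 could move an occasional C2D1 ECG into the Cycle 3 window, hence *essentially* only unscheduled ECGs.

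**3. How many patients have QTcF-triggered ECGs.** Protocol 1.2.1.2.1 reports QTcF above 480 ms in 3.3% of ribociclib patients in the earlier phase III trial. At that rate, 0.033 × 3,000 = 99 patients would have a triggered series.

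**4. Direction of the bias.** This needs assumptions that are not in the documents:

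- baseline QTcF has mean 415 and SD 15 ms, below 450 ms as eligibility requires;
- the mean change μ is 10 or 20 ms, with SD 15 or 20 ms;
- the triggered patients are the top 3.3% by on-treatment QTcF, a simplification of the 481 ms rule;
- a further fraction q (0, 2, 5 or 10%) has an ECG for reasons unrelated to QT, with mean change μ;
- triggered patients keep a fraction r of their change after interruption or dose reduction.

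By simulation, the mean change T in the triggered group is 35.3, 46.9, 45.4 and 57.1 ms for (μ, SD) = (10, 15), (10, 20), (20, 15) and (20, 20). Then:

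row mean = (0.033 × r × T + q × μ) / (0.033 + q)

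all-patient mean = μ − 0.033 × (1 − r) × T

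Example with μ = 10, T = 35.3, q = 0.05:

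- r = 1: row mean (1.165 + 0.5) / 0.083 = 20.1; all-patient mean 10.0; bias +10.1 ms.
- r = 0: row mean 0.5 / 0.083 = 6.0; all-patient mean 10 − 1.165 = 8.8; bias −2.8 ms.

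Range over all combinations:

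| Fraction of change kept (r) | Row mean minus all-patient mean (ms) |
|---|---|
| 1 | +6 to +37 |
| 2/3 | +3 to +22 |
| 1/3 | −4 to +7 |
| 0 | −18.5 to −1 |

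**5. The worst-value rule.** If two ECGs fall in one window, the expected excess of the larger is about 0.564 × within-patient SD. For an assumed SD of 8 to 12 ms this is 4.5 to 6.8 ms, always upward. It also affects the Cycle 2 row, where C1D15 and C2D1 compete.

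**The case against.** A reader might infer that every ECG after C2D1 is taken because of a QT concern, that the late rows therefore hold a few high-risk patients, and that they overstate the QTcF change. The documents do not support this reading, for three reasons.

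First, the EOT ECG is scheduled and has its own row, and discretionary and co-medication ECGs also occur. The text below Table 2-1 puts EOT data into the matching cycle window, but it is written for patient-reported outcomes and its application to ECG is unclear. If it did apply, late rows would also contain patients stopping treatment for any reason.

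Second, repeats under Table 6-5 are taken during interruption or after restart at a lower dose level, so a triggered patient's later values may be smaller. Step 4 gives either sign.

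Third, if QTc prolongation again comes mainly in the first two cycles, the mandated repeats would cluster in the first few windows, and the late rows would rest mostly on other indications.

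It is also fair to say that the stakes are limited. No hypothesis is tested. The special-interest event counts and the notable QTcF categories do not use these means, and the SAP says only that the summary is by timepoint.

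All of this narrows the claim but does not rescue the rows. Selection of unknown direction still prevents a row from standing for the cohort. Adding EOT ECGs would exchange one selected group for a mixture of two.

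**Conclusion.** The point holds as a minor one. Apart from EOT, 15 of the 16 post-baseline cycle windows (Cycle 3 to Cycle 36) hold essentially only unscheduled ECGs, with the worst value kept. They describe a selected, changing subset and cannot be read as the cohort's ECG or QTcF course. This count comes from the two schedules alone and needs no assumption.

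The size and sign of the bias are not established. Selection on high QTcF and the worst-value rule push upward; interruption and dose reduction push downward. The range of −18.5 to +37 ms in step 4 rests wholly on assumed values and shows only that the sign is open. Upward bias is plausible if most of the change persists, but no percentage overstatement can be derived from the documents.

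**What to change.** In SAP 2.8.5.1, replace the reference to the ECOG windows with the scheduled ECG timepoints: summarise change from baseline at C1D15, C2D1 and EOT only. Keep unscheduled ECGs in the notable-value categories and in the listing, both already planned, so no data are lost. If the later rows are retained, show n in each and label them as unscheduled ECGs from a selected subset.

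The same edit gives C1D15 and C2D1 separate rows; at present they share one under the worst-value rule. The two matters can be handled together.

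The cost is a change of SAP wording and the loss of a by-cycle ECG display after Cycle 2.

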#### 2.1.4 Windows for multiple assessments

In order to summarize PRO measures/performance status/vital sign/other data collected over time (including unscheduled visits), the assessments will be time slotted. The following general rule will be applied in creating the assessment windows: If more than one assessment is done within the same time window, the assessment performed closest to the target date will be used. If 2 assessments within a time window are equidistant from the target date, then the earlier of the 2 assessments will be used. If multiple assessments on the same date then the worst case will be used. Data from all assessments (scheduled and unscheduled), including multiple assessments, will be listed.

Novartis	Confidential	Page 17
SAP	22-Feb-2022 (1:27)	CLEE011A2404

The following table provides an example how to define the time windows for Eastern Cooperative Oncology Group (ECOG) performance status (PS).

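### ECG change-by-timepoint table: the Cycle 1 Day 15 and Cycle 2 Day 1 ECGs share one window and the worst is kept, so Day 15 has no row and the Cycle 2 Day 1 QTcF change is shifted upward

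*SAP*

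**What the plan says.** Protocol 7.2.2.6.1 and Table 7-1 schedule ECGs at screening, C1D15, C2D1 and end of treatment. Any others between C2D1 and end of treatment are unscheduled. Protocol 7.1 allows 3 days either side of a visit.

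For the analysis, SAP 2.8.5.1 plans: "Summary statistics will be provided for change from baseline ECG by timepoint". It takes its windows from another assessment: "Time windows for ECG assessment are the same as the time windows for ECOG PS assessment". Within a window: "If more than one assessment is done within the same time window, the worst case will be used".

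That last rule replaces the general one in SAP 2.1.4: "If more than one assessment is done within the same time window, the assessment performed closest to the target date will be used".

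Table 2-1, which SAP 2.8.5.1 adopts, has a baseline row (up to Day 1), then Cycle 2 Day 1 (target Day 29, Days 2 to 42), then Cycle 3 Day 1 (target Day 57, Days 43 to 70), and so on. It has no row for Cycle 1 Day 15.

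**The concern.** Table 2-1 was built for ECOG status, which Table 7-1 does not collect on Day 15. Applied to ECGs, its first window takes in both fixed on-treatment visits, and the worst-value rule then reduces them to one number under the label of the second visit.

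The two visits differ in kind. Under Protocol 6.1.1 ribociclib is given on Days 1-21 and withheld on Days 22-28. The C1D15 ECG is therefore in the planned dosing period, and the C2D1 ECG is at the end of the planned rest days or after them. The table cannot show that contrast. A reader who takes the row label literally will read a worst-of-two value as the QTcF change at Cycle 2 Day 1.

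For patients on schedule, this is the only calendar row that holds fixed-visit ECGs, and QT prolongation is one of the events of special interest in the primary endpoint.

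**Working it through.** **1. Reproduce Table 2-1.** Its target-day formula is d = (k-1)*28+1. For k = 2, 3, 4, 5, 6, 8, 10, 12 it gives 29, 57, 85, 113, 141, 197, 253, 309, matching every listed target. The midpoint of Days 29 and 57 is Day 43, so the first window closes on Day 42, as printed. The calendar rows after baseline number 8 (those cycles) + 8 (k = 15 to 36 in steps of 3) = 16.

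**2. Place the scheduled ECGs (visit day plus or minus 3).**

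| Visit | Days | Table 2-1 row |
|---|---|---|
| C1D15 | 12-18 | Cycle 2 Day 1 (2-42) |
| C2D1 | 26-32 | Cycle 2 Day 1 (2-42) |

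All of these days map to the same row.

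**3. Limits of the overlap.** A C2D1 ECG 13 days late is on Day 29 + 13 = 42 and stays in the row. At 14 days late it is on Day 43 and moves to the Cycle 3 Day 1 row; the C1D15 ECG is then reported alone as Cycle 2 Day 1. Study treatment starts with the first dose of any component (SAP 2.1.3), so letrozole begun L days before ribociclib adds L to both visits. The two still share the row while 32 + L is at most 42, that is, for L up to 10.

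**4. Direction.** Let X be the QTcF change at C1D15 and Y the change at C2D1. With both ECGs in the window the row reports max(X, Y), which is at least Y, and greater than Y whenever X > Y. This needs no distributional assumption. It is claimed for QTcF only, because the SAP does not say which direction is worst for other intervals.

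**5. Size, as illustration.** The documents give no SD for QTcF change and no between-visit correlation. Assume X and Y are normal with a common SD s, correlation r and equal means. Then

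E[max(X, Y)] - mean = s * sqrt((1-r)/pi)

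| s (ms) | r | Excess (ms) |
|---|---|---|
| 10 | 0.7 | 10 * sqrt(0.3/pi) = 3.09 |
| 15 | 0.5 | 15 * sqrt(0.5/pi) = 5.98 |
| 20 | 0.3 | 20 * sqrt(0.7/pi) = 9.44 |

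Simulation with 1,000,000 draws gave 3.07, 5.97 and 9.45.

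**6. Check the remedy.** The midpoint of Days 15 and 29 is Day 22. Giving the midpoint day to the later row, as Table 2-1 does at Day 43, yields C1D15 = Days 2-21 and C2D1 = Days 22-42. Days 12-18 and 26-32 then fall in separate rows. With L days of letrozole lead-in this holds only while 18 + L is at most 21 (L up to 3), and dose interruptions also shift visits. Calendar windows should therefore be the fallback and nominal visit the primary assignment.

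**The case against.** The best defence is that the rule is deliberate. The SAP document history records that the 15 June 2018 amendment specified the ECG change-from-baseline summary and its time windows, and the worst-value rule is stated openly. For a QT safety summary, a prespecified worst-of-window value is conservative, and it is biased only if the row is read as the C2D1 value. It is true that the rule is disclosed. But the table is a summary by visit and its row carries a visit label. Worst-value risk is already covered in the same section by the counts above 450, 480 and 500 ms and the increases above 30 and 60 ms. A footnote would disclose the rule without restoring the Day 15 row.

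It can also be said that the illustration assumes equal true change and that every patient has both ECGs. Both limits stand. A higher true change at Day 15 would enlarge the excess, a lower one would shrink it, and a patient with a single ECG contributes no selection.

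A reader might infer more than the documents support:

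- **That later rows hold only clinically indicated ECGs.** They do not. Protocol Table 6-5 also directs repeats 7 and 14 days after dosing resumes following a QTcF interruption. What holds is that later rows contain no fixed-visit ECGs for patients on schedule.
- **That end-of-treatment ECGs have no clear place.** Table 2-1 has its own row for them: "Assessment taken at the end of treatment visit". The sentence sending such data to the calendar window, "Data obtained at the end of treatment will be classified as other assessment in the corresponding time window", is in a paragraph about PRO data.
- **That same-date repeats have no rule.** SAP 2.1.4 gives one: "If multiple assessments on the same date then the worst case will be used".
- **That QT safety signals are lost.** The notable-value counts are not defined through these windows, events of special interest come from adverse event reports, and every ECG is listed.

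**Conclusion.** The point holds and is minor. For patients on schedule, the table has no C1D15 row, and its Cycle 2 Day 1 QTcF value is the maximum of two visits, so it cannot understate the C2D1 change and will usually overstate its mean. Row placement and direction follow from the documents alone. The 3.1-9.4 ms range rests on assumed SDs, correlations and equal true change, and is not an estimate for this trial. The effect is confined to one descriptive Core Phase table, and no hypothesis is tested.

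**What to change.** In SAP 2.8.5.1, for the change-by-timepoint table:

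- Add a C1D15 row and assign the scheduled ECGs to C1D15 and C2D1 by nominal visit.
- Use Days 2-21 and Days 22-42 as the fallback for unscheduled ECGs, or where nominal visit is missing.
- Apply the closest-to-target rule of SAP 2.1.4 to the by-visit summary.
- Show the worst post-baseline QTcF change as a separate, labelled row.

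The cost is two added rows, a few sentences and a small program change, using data already collected. If the table has already been run, one supplementary table is enough.
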